Stratification and Random Assignment. A key feature of abstinence incentive programs is that participants tend to clearly dichotomize into responders and non-responders. The former initiate and sustain abstinence early in the program, while non-responders, either never initiate abstinence or do so intermittently or for only short periods of time before relapsing. In this study, participants will be stratified into CM responders versus non-responders based on submission of two consecutive weeks of cocaine-

free urines (6 samples) during study weeks 1- 6. Considerable experience with implementing these types of interventions suggests that there will be close to a 50/50 split between responders and non-responders by the end of the first month of the CM program.

By the end of study week 6, all participants still active in the study (and independent of exactly where they may be in the abstinence-contingent lead-In earnings plan) will be randomly assigned to bupropion vs placebo medication from within the responder vs non-responder strata and introduced to their tailored earnings schedule for the remainder of the study (see graphs below). Those who qualify for relapse prevention by submitting 2 weeks of negative urines will be randomized on the day they submit the 6th negative urine, while those who will clearly not qualify for relapse prevention will be randomized at the start of week 6.

Medication: Bupropion.

[figure not shown]
Commercially available sources of Bupropion XL and Microcrystalline Cellulose (placebo) will be obtained by the BPRU pharmacy. Qualified pharmacy staff will prepare double blind dosages by overencapsulation of bupropion tablets. The inert substance in both active and placebo capsules will be Microcrystalline Cellulose. Active or placebo capsules will be placed in one-week blister pack kits compatible with daily dispensing requirements of the protocol. When a medication order is provided to the pharmacy, the blister packs will be labeled with a subject number and dispensed to the study site. Study medication blister-packs may be dispensed to participants by nursing staff at the methadone clinic dispensary window or by BPRU research staff. Each kit would contain an accountability log for clinic or study staff to document distribution of capsules from the kit to the study participant. Medication will be stored either in a secure vault at the methadone clinic site or in a pharmacy-approved safe within a locked room.

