Medication dispensing will begin in study week 1 at which time all participants will begin receiving double blind capsules containing placebo. The advantage of this "placebo run-in" is that it stabilizes the medication taking regimen early in the study, precludes "placebo effects" at the time of random assignment and allows for a smooth transition into the post-random assignment study period without any change in study procedures. Participants may be randomized and potentially switched to active bupropion after giving their 6th cocaine negative urine following placebo initiation (week 3 randomization at the earliest) or at the start of study week 6 for those who provide urinalysis evidence of continued active drug use. Consistent with clinical practice for those randomized to active bupropion, there will be a brief (3-day) induction period followed by maintenance dosing at 300mg/day Medication dispensing will continue through week 30. Typically, only a one week supply will be given, but additional medication may be dispensed for holidays, weather-related or other emergencies.

Abstinence incentive schedule initially drug-negative.

The schematic below (left panel) depicts total weekly earnings for accelerating and decelerating phases for those who submit 6 or more negative urines during the CM run-in. The gradual escalation of voucher values begun in week 1 continues for a total of 12 weeks, which includes the Lead-in phase. Reset contingencies have been included for the relapse prevention participants to forestall early relapse. Once randomized to this condition, a cocaine positive or missing sample submitted prior to week 26 will result in reset to the \$3 value. Following a reset, the participant will earn \$3 then \$3.50 for the first two cocaine negative samples then will return to the most recently achieved point in their earning schedule (e.g. \$11 per sample) after the third consecutive cocaine negative sample. Extending the earning period from 24 to 26 weeks allows for completion of the entire earning schedule with 2 brief (single urine positive) slips during which an additional total of \$13 could be earned.

Abstinence Reinforcement Schedules

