The aim of this study is to evaluate whether bupropion will enhance cocaine abstinence among methadone-maintained patients who are abusing cocaine. This is being evaluated in a double-blind context. Further, based on evidence that individuals with cocaine use disorder typically present to the clinic with a urine sample that is positive for cocaine (which predicts continued use) or negative for cocaine (which predicts abstinence), we had originally proposed to treat those individuals as two separate groups and run 2 parallel studies (presented as Primary Aims 1 and 2), using contingency management as a background platform to support either abstinence or relapse prevention, respectively. Each aim was intended to enroll 100 individuals (N=200) total, to enable equal distribution of bupropion (n=50) and placebo (n=50) within each aim.

Based on unanticipated difficulties with recruitment, we are now collapsing the two parallel studies into the same overarching study, such that Primary Aim 1 will now be examining the effects of bupropion XL vs. placebo on 24-week abstinence outcomes during and after exposure to a behavioral intervention (CM). We are reducing our sample size to 100 individuals, which still preserves the required 50 participants per medication group that was identified in our power analyses as necessary to detect an effect of the medication. This approach will allow us to achieve our primary aim of determining whether bupropion will enhance cocaine abstinence despite challenges with recruitment and will enable this study to still provide clinically important information to advance the treatment of cocaine use disorder.

We are modifying our statistical plan to accommodate this change in sample size. We will retain the original primary outcome measure (biochemically-confirmed abstinence from cocaine), which will be assessed across all participants (independent of abstinence group) in the same statistical model. The endpoint will be binary (abstinent yes or no), and the treatment effect will be assessed using a repeated-measures logistic regression model having two main effects: medication and time, plus their interaction, as

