well as any necessary covariates, including cocaine positive vs negative urine tests prior to random assignment as a covariate. Generalized linear mixed models (GLMM) will be used to analyze repeated measures data, since this technique can include participants with incomplete data without resorting to imputation. This approach has been found to minimize bias and maximize power in cases of incomplete follow-up (see Hedden et al, 2009). Data will then be examined using the nonbinary method described by McCann and Li (2012) in which participants who meet an end of study threshold of success (1 week EOS abstinence) are assigned values indicating their number of beyond threshold weeks of success (in our case 1-24). This distribution will be analyzed as a function of drug condition using a two-sided Vander Waerden two-sample test (Permutt and Berger, 2000).

All other analyses will be conducted in the overarching group that includes those abstinent and actively using at baseline. This approach will allow us to preserve all study Aims with a reduced sample size that will ensure the study can be completed in the time allowed.

The data analysis plan consists of the following:

- 1) Comparison of groups for baseline differences. Participants will be compared as a function of medication group on baseline characteristics to determine whether they are comparable with respect to general demographic features, baseline drug use, and reinforcement measures (drug vs. money relative reinforcing potency scale, Snaith-Hamilton Pleasure scale). Groups will be compared using t tests for continuous measures and chi-square tests for categorical characteristics. If medication groups are found to differ on baseline measures, then these characteristics will be used as covariates in subsequent analyses assessing treatment effect.
 - 2) Primary outcome analyses: (see above)
- 3) Secondary outcome analyses: The main secondary outcome measure will be biochemically-confirmed abstinence from opiates. We hypothesize that participants receiving bupropion will have a higher proportion of opiate abstinent samples as well as for cocaine. Analyses conducted to assess the treatment effect for opiate use will be identical to those used for cocaine use (described above).

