Responsibility for monitoring data and safety during this clinical trial resides with the Principal Investigator (PI) [name] and co-investigator [name], M.D. AE's and SAE's are generally discovered through careful and frequent monitoring of participants by research and clinical staff using open-ended questions about how the participant has been feeling recently. Any complaint is probed for information about frequency, duration and severity, coded on a side-effects checklist and described in a written summary report. The Principal Investigator coordinates the preparation of semi-annual summary reports on the prevalence of side effects and adverse events observed during the course of the study. These reports will be provided annually to the local IRB and to the NIDA Program Official with the annual progress report. The PI will also be responsible for promptly notifying in writing the local Institutional Review Board if a serious adverse event (SAE) occurs. A SAE is defined as either: death; a life-threatening occurrence; hospitalization; new onset significant medical disorder; or significant exacerbation of an existing medical disorder.

In addition an independent panel of consultants will be contracted for bi-annual review of the risks-benefits ratio of the study. At mid-point during enrollment (when 100 randomized participants have completed the study) this panel will be provided with reports of adverse events and with participant outcome data (urine sample results) by unlabeled medication groups (A vs. B), as a function of study assignment (relapse prevention vs abstinence initiation). This information will be used to assess whether the risks reported are considered to be of unusual magnitude or frequency across any specific groups and to determine whether the study should be ended prematurely due to participant safety concerns. It is unlikely that such a small study would be interrupted because of an uneven distribution of adverse events experienced by any one group, however we will ensure that a qualified panel of reviewers makes this decision.

9. Benefits

a. Description of the probable benefits for the participant and for society.

Study participation will directly benefit participants by providing them with methadone maintenance for opioid dependence, with increased urine monitoring beyond that available in usual care and with contingency management that is likely to reduce the amount of cocaine they use.

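### The van der Waerden test leaves out the responder stratum used for randomisation, and the regression covariate is not defined as that stratum; power is lost if the stratum is prognostic

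*Combined protocol and SAP*

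**What the plan says.** Section 4, Stratification and Random Assignment, says that participants will be "stratified into CM responders versus non-responders based on submission of two consecutive weeks" of cocaine-free urines (six samples) in study weeks 1 to 6. The split is expected to be close to 50/50. They are then "randomly assigned to bupropion vs placebo medication from within the responder vs non-responder strata". The text on the incentive schedule for the initially drug-negative group describes that group differently, as "those who submit 6 or more negative urines during the CM run-in".

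Section 6 puts all participants in one repeated-measures logistic model with medication, time, their interaction and any necessary covariates, "including cocaine positive vs negative urine tests prior to random assignment as a covariate". Participants who meet the end-of-study abstinence threshold then receive a value from 1 to 24 weeks, and: "This distribution will be analyzed as a function of drug condition using a two-sided Vander Waerden two-sample test". Item 3 of the data analysis plan repeats both analyses for opiates.

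On prognosis, section 4 states that "participants tend to clearly dichotomize into responders and non-responders". Section 6 describes patients as presenting with a urine that is "positive for cocaine (which predicts continued use) or negative for cocaine (which predicts abstinence".

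**The concern.** The design treats lead-in response as important enough to stratify on, and two separate studies were first planned around this distinction. The rank test then pools everyone and ignores it. If responders and non-responders differ in outcome, that difference stays in the test's error term and hides part of any drug effect. A two-sample rank test has no place for the logistic model's covariate, so the covariate clause cannot repair this.

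The covariate has a problem of its own. With three urines a week for up to six weeks, it could mean the intake urine, the last urine, a proportion of negatives, or the stratum. These are not interchangeable. Responders are randomised on the day of their sixth negative urine, so their last urine is always negative, while a non-responder's last urine can be either.

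**Working it through.** **1. The plan's own figure.** Section 6 says the power analyses required 50 per medication group, but gives no effect size, alpha, power or event rates. The figure cannot be reproduced. As a probe only, the cocaine-positive probabilities that section 3 cites from an earlier bupropion-plus-CM trial (.33 and .57) need 67 per arm for 80% power, two-sided 5%. Fifty per arm gives 68%.

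**2. The two tests.** Scores are normal scores of the ranks, a = Φ⁻¹(R/(N+1)), averaged over ties. Here m is the number on bupropion, n the number in the comparison, and s² the variance of the scores (divisor n).
- Unstratified: T = Σ over bupropion of (a − ā); V = m(n − m)s²/(n − 1); z = T/√V.
- Stratified: the same T and V computed inside each stratum and summed over the two strata.

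**3. Where the loss arises.** Let R² be the share of score variance lying between strata. With simple allocation, chance imbalance of the strata moves T. The test keeps its 5% level but carries noise that stratifying would remove. With allocation balanced within strata, the true null variance is about (1 − R²)V, so the actual level is 2Φ(−1.96/√(1 − R²)). A simulation with exact balance gave these R² values under no drug effect:
- 60%/20%, R² = 0.150: 1.96/√0.850 = 2.13, level 3.4% (simulated 3.5%)
- 70%/15%, R² = 0.266: 1.96/√0.734 = 2.29, level 2.2% (simulated 2.2%)
- 80%/10%, R² = 0.410: 1.96/√0.590 = 2.55, level 1.1% (simulated 0.9%)

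**4. Main simulation.** From the plan: N = 100, strata about 50/50, 1:1 allocation, two-sided test. Assumed: alpha 5%, no dropout, odds ratio 3 in both strata, and score 0 for participants below the threshold (the plan gives them no value). Successes have weeks uniform on 1–24 in both strata (equal runs), or 6–24 in responders and 1–18 in non-responders (longer runs). Allocation is simple or in blocks of 4. There were 6,000 trials per scenario, and 8,000 for the matching sample sizes. Losses are in percentage points and cover both allocation methods and two ways of scoring the stratified test (pooled or within-stratum ranks).

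| Placebo success, responders/non-responders | Loss, equal runs | Loss, longer runs | Example: unstratified vs stratified power (simple allocation, longer runs) | N for the unstratified test to match (simple allocation) | Type I error, unstratified, blocks of 4 |
|---|---|---|---|---|---|
| 30%/30% | none | none | 68% vs 68% (simple allocation) | – | 5.0–5.1% |
| 40%/20% | 1–2 | 3–4 | 60% vs 64% | 104–108 | 3.3–4.6% |
| 50%/15% | 4–6 | 8–10 | 49% vs 57% | 110–123 | 3.1–3.7% |
| 60%/10% | 8–12 | 12–16 | 36% vs 48% | 125–140 | 1.9–2.3% |

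With simple allocation the unstratified type I error was 4.4–5.5% throughout.

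**5. Other rates.** The exact-balance simulation in step 3 (equal runs, odds ratio 3) gave, unstratified to stratified: 67% to 67% at 40%/40%; 62% to 63% at 50%/30%; 51% to 55–56% at 60%/20%; 36% to 44–46% at 70%/15%; 17% to 29–32% at 80%/10%.

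**6. The covariate.** A logistic model of a single binary endpoint (not the planned mixed model) was run at 60%/20% and odds ratio 3. Power was 69% with the stratum, 66% with the last urine before randomisation, 63% with the intake urine and 65% with no covariate. This assumes a negative last urine in all responders and 25% of non-responders, and a positive intake urine in 85% and 97%. It shows only that the definition matters.

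**The case against.** The strongest reply is that the covariate probably already is the stratum. The headings of the two incentive schedules call the groups initially drug-negative and initially drug-positive, and section 6 introduces the covariate while merging those two groups. That is a fair reading. On it the logistic model loses nothing, and the covariate needs only a definition. The difference between the two descriptions of the stratum is likewise a clarification.

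The logistic model is also the main analysis, and the rank test follows it. That stands and limits what is at stake, although the rank test belongs to the primary outcome analyses and is repeated for opiates.

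The fall from 200 to 100 participants did not halve this comparison. Each original aim was 50 versus 50, and so is the merged one. That also stands.

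The gap between strata is assumed. The statement about prediction concerns the urine at presentation, the dichotomy concerns behaviour during incentives, and only responders face declining payments, which could narrow the gap by the end. At 30%/20% the loss was about 0 to 2 points. The size is therefore uncertain, but stratifying costs almost nothing if the gap is small.

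Finally, the gain can depend on how the stratified test is scored when the effect lies in one stratum only. With odds ratio 4 in responders only, at 50%/15%, power was 41% with pooled scores, 32% with within-stratum scores and 31% unstratified. With odds ratio 5 in non-responders only, at 40%/20%, it was 29%, 39% and 29%. So the scoring must be chosen in advance. Neither version fell materially below the unstratified test.

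The rule that adjusts for observed baseline differences does not help: stratified randomisation tends to prevent such a difference, and a two-sample test cannot take a covariate.

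**Conclusion.** The concern holds. The van der Waerden test omits the factor used for randomisation, and the regression covariate is not tied to it. The consequence is lost efficiency in the rank test, not a false-positive risk. The loss ranges from nothing to 16 percentage points across the placebo rates in the main table, and is 4 to 10 points in its middle case of 50%/15%. These sizes depend on assumed stratum rates, run lengths, a common odds ratio of 3, alpha of 5% and no dropout. Only the direction follows from the design. The test is conservative as well if allocation is balanced within strata, but the documents do not say whether it is blocked. The change should be made, though the trial's validity does not depend on it.

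**What to change.** - Define the logistic-model covariate as the responder/non-responder stratum as randomised, and include it whatever the baseline comparisons show.
- Stratify the van der Waerden test by it, either by summing the score statistic and its variance over strata or by permuting within strata. Name pooled or within-stratum scores before unblinding.
- State how allocation is done within strata.
- Reconcile the two descriptions of the stratum in section 4, so that it has one meaning in the analysis.

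The cost is wording in the statistical section. The stratum is known at randomisation, so no new data are needed. Section 7, Risks Management, already has outcome data reported to the review panel "as a function of study assignment (relapse prevention vs abstinence initiation"), although its trigger of 100 completers as the mid-point appears to date from the 200-participant design. The downside is close to nil: with equal stratum rates both tests had 68% power.

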Official Title: Medication Enhanced CM for Cocaine Dependence

NCA Number: 02111798

Document Date: January 2, 2019

Date: January 2, 2019

Principal Investigator: [name].

Application Number: NA00090062

JHM IRB - eForm A - Protocol

• Use the section headings to write the JHM IRB eForm A, inserting the appropriate material in each. If a section is not applicable, leave heading in and insert N/A.

 When submitting JHM IRB eForm A (new or revised), enter the date submitted to the field at the top of JHM IRB eForm A.

1. Abstract

Provide no more than a one page research abstract briefly stating the problem, the research hypothesis, and the importance of the research.

The efficacy of behavior therapies may be enhanced by certain medications, particularly those that act on dopaminergic systems. This project will examine effects of bupropion on initiation and maintenance of cocaine abstinence in a population of cocaine dependent methadone maintenance patients. Bupropion appears to be the most promising medication for this purpose because of its previously demonstrated efficacy and safety as well as its pharmacological actions at dopamine systems.

Methadone maintained cocaine dependent study participants (N = 100) will be stratified according to whether or not they stop their cocaine use during initial exposure to an abstinence incentive (contingency management) procedure and will be randomly assigned to receive bupropion XL (300mg/day) versus placebo for the remainder of the study. Our hypothesis is that bupropion as compared to placebo treatment will both enhance rates of abstinence initiation in those who have difficulty stopping cocaine and retard rates of relapse in those who initially stopped their cocaine use.

Participants will receive a CM schedule that is tailored to their initial CM response and outcomes will be tracked over a 6-month time frame that includes assessment of drug use outcomes after incentives have stopped. In addition, the project will provide novel information about mechanisms of medication effects by measuring subjective drug effects, drug vs money choices, and self-reports of pleasure derived from daily non-drug activities. We hypothesize that bupropion compared to placebo participants will report non-drug activities as more pleasurable (reinforcing), will engage in more of them and that measures of non-drug reinforcement will mediate abstinence outcomes.

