Overall, this research will provide new and valuable information about combined behavioral-pharmacological treatments and specifically the conditions under which medication may enhance effects of CM. If hypothesized synergies can be demonstrated, the study will point the way to a significant advance in improved treatment outcomes for this critical group of drug abusers. The proposed study is compelling because it conceptually differentiates the two key clinical issues in treatment of stimulant abusers- abstinence initiation and relapse prevention. It uses a design that efficiently and effectively tests a combined treatment approach for each clinical issue and as well examines cognitive function and reinforcement-based mediators. The research will add to understanding of the interplay between brain reinforcement systems and drug-seeking behavior. Finally, it will make an important contribution to behavioral therapy development by exploring a novel solution to limitations previously noted for CM that include lack of response in some patients and relapse after withdrawal of incentives.

2. Objectives (include all primary and secondary objectives)

Specific aims of the project are the following:

- a. Examine in those who initially achieve abstinence with CM the effects of bupropion XL (300 mg/day) versus placebo on 24-week abstinence outcomes during and after CM. Hypothesis: Among participants who achieve initial abstinence, those treated with bupropion compared to placebo will have significantly longer delays to resumption of drug use and higher rates of abstinence at 24-weeks.
- b. Examine in those who initially fail to achieve abstinence with CM the effects of active bupropion XL (300 mg/day) versus placebo medication on subsequent abstinence initiation outcomes. Hypothesis: Among participants who failed to achieve initial abstinence, those treated with bupropion vs placebo will have significantly higher rates of abstinence at 12 and 24 weeks.
- c. Identify mechanisms of bupropion-enhanced outcomes by administering self-report instruments that assess response to non-drug reinforcement.

 Hypothesis1: Bupropion compared to placebo participants will report both money and non-drug activities as more reinforcing and will engage in more of the latter.
 - Hypothesis 2: Enhanced non-drug reinforcement will mediate abstinence outcomes

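### Aims a and b still state separate responder and non-responder hypotheses, but every planned analysis is pooled, so the statement that all aims are preserved does not hold for them as written

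*Combined protocol and SAP*

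**What the plan says.** Section 6 (Sample size and power) explains that the trial was first planned as two parallel studies of 100 people each, "to enable equal distribution of bupropion (n=50) and placebo (n=50) within each aim". After recruitment difficulties these became one study of 100, and "Primary Aim 1 will now be examining the effects of bupropion XL vs. placebo on 24-week abstinence outcomes" during and after CM. Abstinence is to be "assessed across all participants (independent of abstinence group) in the same statistical model". The model is a repeated-measures logistic regression with medication, time and their interaction, and cocaine urine status before randomisation enters as a covariate. A second analysis gives participants who are abstinent at the end of the study a count of weeks of success. "This distribution will be analyzed as a function of drug condition", by a Van der Waerden test. Section 6 then assigns every remaining analysis to the combined group and concludes: "This approach will allow us to preserve all study Aims with a reduced sample size".

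The abstract, which already carries N = 100, still predicts that bupropion will both "enhance rates of abstinence initiation in those who have difficulty stopping cocaine and retard rates of relapse in those who initially stopped". In section 2, aim a reads: "Among participants who achieve initial abstinence, those treated with bupropion compared to placebo will have significantly longer delays to resumption of drug use", and adds higher abstinence at 24 weeks. Aim b reads: "Among participants who failed to achieve initial abstinence, those treated with bupropion vs placebo will have significantly higher rates of abstinence". Its time points are weeks 12 and 24.

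Section 3 (Background) presents the design as answering the initiation and relapse-prevention questions at the same time. Section 4 (Contingency management summary) says the responders' payment schedule was built to assess time to relapse.

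**The concern.** Two hypotheses about two strata are stated as aims, and no analysis in the plan addresses either stratum. A reader of sections 1 to 4 expects one answer on starting abstinence and another on avoiding relapse. A reader of section 6 finds one pooled answer, together with an assurance that nothing was lost. It is then unclear whether aims a and b are confirmatory, exploratory or withdrawn.

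Followed exactly, the plan does not say in which stratum an effect occurred, and it does not estimate delay to resumption. If stratum results are reported anyway because the aims call for them, some analytic choices could be made after the data are seen. This matters most for time to resumption, which has no model, event definition or missing-urine rule.

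**Working it through.** **1. The plan's own figure.** Superseded design: 2 aims × (50 + 50) = 200. Current design: 100 / 2 = 50 per medication group. So 50 per arm is arithmetically kept for the pooled comparison. The power calculation behind it cannot be reproduced, because the document gives no alpha, power, effect size, control rate, within-person correlation or dropout.

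**2. Each hypothesis against the planned analyses (section 6).**

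- *Aim a, 24-week abstinence in responders.* The binary endpoint, the model with medication-by-time, and the use of incomplete data without imputation are all given. Only the stratum term or subset is missing.
- *Aim b, 12- and 24-week abstinence in non-responders.* The same applies.
- *Aim a, delay to resumption in responders.* No model, event definition or missing-urine rule is given. Section 4 treats a single positive urine as a brief slip for payment purposes, so what counts as resumption is open.
- *Covariate for urine status before randomisation.* Adjustment gives one common medication effect, not one per stratum. The text also does not say that this covariate is the randomisation stratum of section 4 (two consecutive weeks, six samples, cocaine-free in weeks 1 to 6).
- *Weeks-of-success analysis.* It is pooled by drug condition and gives values only to those abstinent at the end. As described, a responder who resumes early and one who resumes late both miss the threshold if both are using at the end. It does not estimate delay to resumption.
- *Independent panel (section 7, Risks Management).* Outcomes by unlabelled medication group and study assignment go to the panel for safety review. This is not a test of either aim.

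**3. Stratum sizes.** Section 4 expects close to a 50/50 split. Section 3 says about half or fewer respond, so a responder share of 30% to 50% is taken as an assumed range.

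- Responders per arm: 50 × 0.3 = 15, up to 50 × 0.5 = 25.
- Non-responders per arm: 50 × 0.7 = 35, down to 50 × 0.5 = 25.

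**4. Precision for a difference in abstinence.** The half-width of the 95% interval is 1.96 × √(2p(1−p)/n), with n per arm, one outcome per person and no dropout.

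| n per arm | p = 0.2 or 0.8 | p = 0.5 |
|---|---|---|
| 50 (pooled) | 1.96 × √(0.32/50) = 0.157 | 1.96 × √(0.5/50) = 0.196 |
| 25 (even split) | 1.96 × √(0.32/25) = 0.222 | 1.96 × √(0.5/25) = 0.277 |
| 15 (30% responders) | 0.286 | 0.358 |
| 35 (70% non-responders) | 0.187 | 0.234 |

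**5. Precision for time to resumption (assumption-based).** There are 30 to 50 responders in total. If 50% to 80% resume (assumed), events run from 30 × 0.5 = 15 to 50 × 0.8 = 40. The 95% limits for a hazard ratio are the estimate divided by, and multiplied by, exp(1.96 × √(4/events)). This factor is 2.75 at 15 events and 1.86 at 40, so about 1.9 to 2.8.

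**The case against.** The strongest reply is that section 6 governs and is not ambiguous. It says openly that the studies are merged, redefines the primary aim and pools everything else. The abstract and section 2 then merely hold stale wording. Read directly after that redefinition, the sentence about preserving the aims can naturally mean the new pooled aim plus the remaining ones. This stands as far as it goes: the governing analysis is clear, and the sentence is loose rather than plainly false. But section 6 never withdraws or demotes the responder and non-responder hypotheses, and the abstract carries the reduced sample size alongside them.

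A second reply is that relapse is still covered, since section 3 describes the weeks-of-success method as having shown a relapse-delay effect in a re-analysis of a methamphetamine trial. The plan does keep a sustained-abstinence outcome, so it would be wrong to infer that relapse prevention was dropped altogether. The pooled test still gives no responder-only result.

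A third reply is that, if the plan is followed exactly, no stratum analysis is run and no choice is made after seeing data. That is correct. The risk arises only if the stated aims are reported on despite section 6. Nor should a reader infer that the plan lacks a model or incomplete-data approach in general: section 6 supplies both for binary abstinence.

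Finally, the textual mismatch does not depend on the precision figures. They serve only to show how stratum results should be labelled.

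**Conclusion.** The point holds as an inconsistency that should be fixed. Aims a and b, as written, have no matching analysis, and the statement that all aims are preserved is true only under a reading that the text does not give.

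A reader might infer that the merger undermines the primary comparison, or that the stratum hypotheses are themselves after-the-fact. The documents support neither. The pooled test and its 50 per arm are unaffected, and the hypotheses, their direction and the strata are all stated in advance. What is missing is the stratum analysis for binary abstinence and the whole analysis for time to resumption.

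On size, an even split leaves about 25 per arm per stratum and an interval of about ±22 to 28 points, against ±16 to 20 pooled. With 30% responders it would be about ±29 to 36 in responders and ±19 to 23 in non-responders. These figures assume equal arms within strata, rates of 20% to 80%, one outcome per person and no dropout. They do not describe the planned repeated-measures model, but they are enough to show that stratum results could only be exploratory.

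**What to change.** 1. Restate the abstract's hypothesis and aims a and b as one pooled confirmatory aim that matches section 6, with responder and non-responder effects labelled exploratory.
2. Replace the sentence on preserving all aims with a statement that 50 per arm covers the pooled comparison only, and that each stratum will have about 25 per arm if the near-even split holds. Give the expected interval width.
3. Pre-specify two exploratory, low-powered outputs from urines already collected: (i) medication effects with 95% confidence intervals by the randomisation stratum of section 4, through a medication-by-stratum term in the planned model; and (ii) time from randomisation to resumption of cocaine use in responders, with the event and the handling of missing urines defined before unblinding.

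Steps 1 and 2 alone cure the inconsistency, and they cost only wording in the abstract, objectives and statistics section. Step 3 adds two outputs and no patients, visits or samples. The downside is wide stratum intervals and more modest claims about initiation and relapse prevention.
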